
Table 1. The Detailed Analysis Visit Windows For Pk.....	15
Table 2. The Detailed Analysis Visit Windows For Vital Signs.....	15
Table 3. The Detailed Analysis Visit Windows For Ada.....	15
Table 4. The Detailed Analysis Visit Windows For Clinical Lab Assessment.....	16
Table 5. Objectives And Endpoints	22

LIST OF ABBREVIATIONS

List abbreviations and definitions of specialized or unusual terms, measurements, or units. Examples are provided below. These can be modified at study level.

Abbreviation or Specialized Term	Definition
ADA	Antidrug Antibody
AE	Adverse event
AESI	Adverse Event of Special Interest
AUC ₀₋₁₅₀	Area under the serum concentration-time curve from time zero to 150 days
ATC	Anatomic Therapeutic Chemical
BLQ	Below the limit of quantitation
BMI	Body mass index
C _{max}	Observed maximum serum concentration
CRF	Case Report Form
CSP	Clinical Study Protocol
CSR	Clinical Study Report
DBL	Database Lock
ECG	Electrocardiogram
IM	Intramuscular
IP	Investigational Product
IPD	Important Protocol Deviation
NOCD	New Onset Chronic Disease
PDMP	Protocol Deviations Management Plan
PK	Pharmacokinetics
RSV	Respiratory syncytial virus
Q1	First quartile
Q3	Third quartile
SAE	Serious adverse event
SAP	Statistical Analysis Plan
SD	Standard deviation
TEAE	Treatment-Emergent Adverse Event
TESAE	Treatment-Emergent Serious Adverse Event
T _{max}	Time to maximum observed concentration

AMENDMENT HISTORY

CATEGORY Change refers to:	Date	Description of change	In line with CSP?	Rationale
N/A	12-Apr-2021	Initial approved SAP	N/A	N/A

2.0	20-Dec-2021	
Updated the description of the definition of as-treated population in section 3.2 to align with CSP, and clarified ADA analysis will be performed in this population.
 
Added description of decimal places in terms of data presentation in section 3.3.
 
Clarified the baseline definition for blood pressure and heart rate in 3.3.1.2.
 
Added the description for the reporting and presentation of COVID-19 related protocol deviations and issues in sections 3.3.5 and 4.1.3.2.
 
Updated the presentation of subjects screened but not randomized in subject disposition summary in section 4.1.1.2.
 
Clarified algorithm for partial AE start date imputation in appendix.
 
Combined section 4.1.7 with section 4.1.6, for the presentation of medical and surgical history, and updated numbering for subsequent sections.
 
Updated the presentation for allergy history and procedures in section 4.1.7 and 4.1.10.
 
Updated section 4.1.5.2 to remove the presentation of categorical variables since baseline characteristics only include height, weight, and BMI.
 
Updated the analysis of ADA in section 4.2.2.1.4.
 
Removed the summary table for TEAE with outcome fatal; clarified which lab parameters will be graded by CTCAE; removed weight and BMI in the presentation of vital signs in section 4.2.2.4.
	Yes, CSP Amendment 1	N/A
-----	-------------	--	----------------------	-----

1 INTRODUCTION

This is the statistical analysis plan (SAP) for study D5290C00007. The SAP expands on the statistical analyses specified in the Clinical Study Protocol (CSP). Any changes to any specifications in the CSP will be described in Section 2 of this document.

This SAP is based on the CSP Version Amendment 1, dated 04 December 2020.

1.1 Study objectives

1.1.1 Primary objective

- The primary objective of this study is:
 - To evaluate serum concentrations of nirsevimab.

1.1.2 Secondary objective

- The secondary objective is:
 - To evaluate the safety and tolerability of nirsevimab when administered as a single fixed IM dose of 300 mg to healthy Chinese adult subjects.
 - To evaluate ADA responses to nirsevimab in serum.

1.2 Study design

[figure not shown]
Study D5290C00007 is a Phase 1, randomized, double-blind, placebo-controlled study to evaluate the pharmacokinetic (PK), safety, and tolerability of nirsevimab compared to placebo when administered as a single fixed IM dose of 300 mg to healthy Chinese adult subjects. Enrollment is planned at a single study center in China.

Approximately 24 healthy Chinese subjects will be randomly assigned in a 3:1 ratio to receive nirsevimab (n = 18) or placebo (n = 6). All subjects will be followed for approximately 150 days after dosing to assess safety, pharmacokinetics (PK), and antidrug antibody (ADA) response. Serum concentration of nirsevimab at selected time points will be evaluated as the primary endpoint to confirm that adequate serum exposures are maintained at least 5 months after dosing (ie, through Day 151; over a RSV season).

ADA will be measured at selected time points throughout the study up to Day 151.

Safety endpoints include TEAEs, TESAEs, AESIs (defined as hypersensitivity including anaphylaxis, immune complex disease, and thrombocytopenia), NOCDs, clinical laboratory assessments and vital signs.

Figure 1 Study Flow Diagram

ADA = antidrug antibody; IM = intramuscular; PK = pharmacokinetics.

1.3 Number of subjects

This study will randomize approximately 24 subjects of whom approximately 18 will receive nirsevimab and approximately 6 will receive placebo. Because all analyses will be descriptive in nature and no hypothesis is being tested statistically, no formal sample size calculation was performed. Current sample size and sampling scheme are selected to facilitate estimation and numerical comparison of C_{max} , time to maximum observed concentration (T_{max}), and area under the concentration-time curve from time 0 to 150 days (AUC_{0-150}) between Chinese and non-Chinese adult subjects.

2 CHANGES TO PROTOCOL PLANNED ANALYSES

Not applicable.

3 DATA ANALYSIS CONSIDERATIONS

3.1 Timing of Analyses

There will be no interim analysis for this study. A final analysis will be conducted when all subjects have completed the last visit of the study (Day 151).

The final analysis will be performed by IQVIA Biostatistics and PK Biostatistics teams following sponsor authorization of this SAP, database lock and sponsor authorization of analysis sets.

3.2 Analysis Populations

Two analysis sets will be considered in this study:

PK Population

The PK population will include all subjects who have received any dose of investigational product (IP), and have at least one measurable postdose serum PK observation and for whom PK blood samples are assumed not to be affected by factors such as important protocol deviations (to be determined prior to unblinding). Pharmacokinetic analyses will be based on the PK population. Subjects who receive placebo will not be part of the PK population.

As-treated Population

All subjects who are randomized into the study and who received any amount of IP will be included in the as-treated population. All safety and ADA summaries will be based on this analysis set and all subjects will be analyzed according to the actual treatment received.

3.3 General Considerations

Statistical summaries and analyses will be performed by IQVIA under the direction of the Biostatistics Group, AstraZeneca using SAS® Version 9.4 or higher and, where appropriate, additional validated software.

No statistical tests will be conducted in this study. For continuous variables, descriptive statistics will include the number of subjects (n), mean, standard deviation, median, minimum and maximum. When needed, the use of other percentiles (e.g. Q1 and Q3) will be mentioned in the relevant section. Frequencies and percentages will be displayed for categorical data. The denominators for all percentages will be defined as the number of non-missing values for each variable within the analysis set. Percentages will be presented with 1 decimal place. If the original data has N decimal places (if original data has more than 2 decimal places, then N= 2), then the summary statistics except for PK variables should have the following decimal places:

- Minimum and maximum: N
- Mean, median: N + 1
- SD: N + 2

Summaries will be presented within either PK population or as-treated population depending on the endpoint, unless specifically stated otherwise.

Nirsevimab serum concentrations and serum PK parameters will be summarized using descriptive statistics (e.g., n, arithmetic mean, SD, geometric mean, geometric SD, geometric coefficient of variation (CV%) minimum, median, and maximum).

The geometric mean is calculated as the exponential of the arithmetic mean calculated from data on a log scale. The geometric CV% is calculated as $100 \cdot \sqrt{(\exp(s^2) - 1)}$ where s is the SD of the data on a log scale. For T_{\max} only n, median, minimum, and maximum will be reported.

Individual PK concentration versus actual time plots will be presented on linear and semi-log scales. Mean PK concentration versus scheduled sampling time plots will also be presented on linear and semi-log scales.

- All serum concentration data will be reported and analyzed with the same precision as the source data regardless of how many significant figures or decimals the data carry. Derived PK parameters will be rounded for reporting purposes both in the summary tables and by-subject listings. For the calculation of descriptive statistics and the statistical analysis, rounded PK parameter values as presented in the data listings will be used. For derived PK parameters, C_{\max} will be reported and analyzed with the same precision as the source data, others will be reported and analyzed with 2 decimal places.

Reporting of mean, SD, minimum, median, and maximum will follow the rounding convention of the individual PK variables. Coefficient of variation will always be reported to 1 decimal place.

3.3.1 General Study Level Definitions

3.3.1.1 Reference Start Date and Study Day

Study Day will be calculated from the reference start date, and will be used to show start/stop day of assessments and events.

Reference start date (Day 1) is defined as the day on which the study medication is administered, and will appear in every listing where an assessment date or event date appears. There is no day 0 in this study.

- If the date of the assessment/event is on or after the reference start date then:

Study Day = (date of assessment/event – reference start date) + 1.

- If the date of the assessment/event is prior to the reference start date then:

Study Day = (date of assessment/event – reference start date).

In general, listings will present the actual partial or missing values rather than the imputed values that may be used in derivation. In instances where imputed values will be presented, imputed values will be flagged. Actual rules will be fully defined in the mock-up tables, figures, and listings document. For example, where day or month is missing from the date recorded, but is required in the calculation of time to first dose, e.g. from first diagnosis or clinical laboratory tests, day and/or month will be imputed as 01 i.e. 1st of the month or 1st January. Otherwise no imputations will be made for any missing data, unless agreed by the study team. In the situation where the event date is partial or missing, the Study Day and any corresponding durations will appear partial or missing in the listings. If a date is partial, no imputation will be done except for adverse events (AEs).

3.3.1.2 Baseline

Unless otherwise specified, baseline is defined as the last non-missing measurement taken prior to the administration of study treatment (including unscheduled assessments).

Additionally, baseline measurements of systolic, diastolic blood pressure and heart rate should come from the same assessment, and the average of two readings within schedule prior to dosing will be taken as a baseline.

Change from baseline will be defined as the post-baseline value minus the baseline value.

3.3.2 Analysis Visit Window

For the visit-based summaries for PK, ADA, vital signs, and clinical laboratory data, the summaries will be based on the scheduled days with adjusted analysis visit windows. The analysis visit windows will be based on the collection schedule listed in the protocol and summaries will be windowed to the closest scheduled visit for those data. Visit windows have been constructed so that every observation collected can be allocated to a particular visit. However, all data will be included in the listings. If multiple readings are recorded within a single analysis visit window, the following rules will apply:

- If there are 2 or more valid, non-missing observations within the same visit window, and
 - if they are on different days, then the non-missing one which is closest to the scheduled visit day will be used in the analysis.

- if 2 or more valid observations are on different days but equidistant from the scheduled visit, then the non-missing observation with the earlier collection date will be used in the analysis.
- if 2 or more valid, non-missing observations are on the same day which is closest to the scheduled visit day, and have a different assessment time, then the earlier one will be used in the analysis.
- For the visit-based summaries for ADA, if both ADA positive and negative samples are available within a subject's visit, ADA positive will be reported.
- If a visit window does not contain any observations, then the data will remain missing.

The detailed analysis visit windows are summarized between table 1 to table 4 as below:

Table 1. The detailed analysis visit windows for PK:

Scheduled Study Day	Scheduled time relative to dosing	Analysis Windows
Day 1 (pre-dose)	Pre-dose	Any time prior to dosing
Day 2	24 h (1 day)	±2h
Day 4	72h (3 days)	±4h
Day 6	120 h (5 days)	±6h
Day 8	168 h (7 days)	±8h
Day 15	14 days	±1d
Day 31	30 days	±2d
Day 91	90 days	±5d
Day 151	150 days	±10d

Table 2. The detailed analysis visit windows for vital signs:

Scheduled Study Day	Analysis Windows
Day 1 (post-dose)	Study Day = 1
Day 2	$2 \leq \text{Study Day} \leq 3$
Day 6	$4 \leq \text{Study Day} \leq 10$
Day 15	$11 \leq \text{Study Day} \leq 22$
Day 31	$23 \leq \text{Study Day} \leq 60$
Day 91	$61 \leq \text{Study Day} \leq 120$
Day 151	$121 \leq \text{Study Day}$

Table 3. The detailed analysis visit windows for ADA:

Scheduled Study Day	Analysis Windows
Day 1 (pre-dose)	Study Day = 1
Day 31	$2 \leq \text{Study Day} \leq 60$
Day 91	$61 \leq \text{Study Day} \leq 120$
Day 151	$121 \leq \text{Study Day}$

Table 4. The detailed analysis visit windows for clinical lab assessment:

Scheduled Study Day	Analysis Windows
Day 6	$2 \leq \text{Study Day} \leq 10$
Day 15	$11 \leq \text{Study Day} \leq 22$
Day 31	$23 \leq \text{Study Day} \leq 60$
Day 91	$61 \leq \text{Study Day}$

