- Diastolic blood pressure (mmHg)
- Pulse rate (BPM)
- Respiratory Rate (resp/min)
- Temperature (°C)
- Temperature location
 - Oral
 - Tympanic
 - Rectal
 - Axillary
 - Temporal

Vital signs data obtained up until the 151 day safety follow-up visit will be included in the summary tables. Vital sign values and change from baseline (applicable to post baseline measurements) will be summarized by each scheduled time-point. All observed vital signs results will be listed. Worst post-baseline increase is defined as maximum increase compared to baseline, and worst post-baseline decrease is defined as maximum decrease compared to baseline. Both worst changes will be listed as well.

The denominator in vital signs data should include only those subjects with recorded data.

Vital Signs will be presented by treatment group. Systolic and diastolic BP, pulse rate, respiratory rate and temperature will be listed by subject and summarised using standard summary statistics (mean, SD, minimum, Q1, median, Q3, maximum, and number of subjects) for the observed value and change from baseline at each scheduled study visit.

Markedly abnormal quantitative vital signs measurements will be identified in accordance with the following predefined markedly abnormal criteria:

Parameter	Unit	Lower limit	Upper limit
Diastolic blood pressure	mmHg	60	90
Systolic blood pressure	mmHg	90	140
Pulse rate	Beats/min	50	100
Body temperature	Celsius	36.0	37.5
Respiratory rate	Breaths /min	8	20

Pregnancy

Pregnancy information are collected in “Pregnancy Test Urine” and “Pregnancy Report” CRF page and will be listed for as-treated population.

Increased Liver Biochemistry and Evaluation of Hy’s Law

Cases where a subject shows elevations in liver biochemistry may require further evaluation and occurrences of AST or ALT $\geq 3 \times$ ULN together with total bilirubin (TBL) $\geq 2 \times$ ULN may need to be reported as SAEs.

A potential Hy’s Law (PHL) case is defined as aspartate aminotransferase (AST) or alanine aminotransferase (ALT) $\geq 3 \times$ upper limit of normal (ULN) together with total bilirubin (TBL) $\geq 2 \times$ ULN at any point during the study following the start of investigational product irrespective of an increase in alkaline phosphatase (ALP).

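### The Day 1 post-dose vital-signs window has no time-of-dose condition, so a pre-dose reading on the dosing date, if one is taken, would fill the post-dose row

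*SAP*

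**What the plan says.** - **Window.** In SAP Section 3.3.2, Table 2, the first row label begins "Day 1 (post-dose" and its window is Study Day = 1. Table 2 has no Day 1 pre-dose row.
- **Study Day.** Section 3.3.1.1 states "Reference start date (Day 1) is defined as the day on which the study medication is administered". On or after that date, "Study Day = (date of assessment/event – reference start date) + 1". Only dates enter the formula.
- **Tie rule.** Section 3.3.2 covers two or more valid readings sharing a date: "which is closest to the scheduled visit day, and have a different assessment time, then the earlier one will be used in the analysis". The only endpoint-specific exception is for ADA.
- **Allocation.** The same section says "Visit windows have been constructed so that every observation collected can be allocated to a particular visit".
- **Baseline.** Section 3.3.1.2 gives the general rule: "baseline is defined as the last non-missing measurement taken prior to the administration of study treatment (including unscheduled assessments". For blood pressure and heart rate, "the average of two readings within schedule prior to dosing will be taken as a baseline". It does not say on which day those two readings are taken.
- **Output.** Section 4.2.2.4 says "Vital sign values and change from baseline (applicable to post baseline measurements) will be summarized by each scheduled time-point".
- **Collection.** Section 4.2.2.1.3 lists screening, Day -1 and Day 1, and refers to the protocol tables for the details.

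**The concern.** The label of the Table 2 row and the rule that fills it do not agree. The label restricts the row to readings after the injection, but the window admits the whole calendar day. The tie rule then prefers the earliest reading of that day. A program written from the window column and the tie rule would pick a pre-dose reading whenever one exists on the dosing date.

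Vital signs are a named secondary safety endpoint, and Day 1 is the only row of the by-visit summary that covers the hours after the injection. If that row holds pre-dose values, it compares pre-dose with pre-dose and cannot show an acute change in either arm. Two programmers could also produce different Day 1 tables from the same text.

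**Working it through.** The SAP gives no figure on this point, so there is nothing to reproduce. The check applies the written rule to the possible schedules.

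**Step 1: does a pre-dose reading on the dosing date enter the window?** Date of assessment minus reference start date = 0, so Study Day = 0 + 1 = 1. It satisfies Study Day = 1.

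**Step 2: does the window expression itself imply post-dose?** No. Table 3 uses the identical expression for its ADA pre-dose row. Table 1 (PK) bounds its pre-dose row by the dose, so a dose-relative condition was available and was not used in Table 2.

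**Step 3: which reading is kept?** Within Study Day 1 all readings are equally close to the scheduled day, so the earlier one is used. A pre-dose reading precedes every post-dose reading.

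**Step 4: effect on change from baseline.** Let R1 and R2 be two pre-dose readings in time order, P the first post-dose reading, d the true acute shift and s the within-subject SD. Assumptions not in the SAP: d from -20 to +20 units, s = 3 or 6, independent errors, and no drift between R1 and R2.

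| Where the pre-dose readings fall | Selected | Change vs mean of R1, R2 | Change vs last pre-dose reading |
|---|---|---|---|
| A. Both on Day 1 | R1 | (R1 - R2)/2: mean 0, SD s/√2 = 2.1 or 4.2 | R1 - R2: mean 0, SD s√2 = 4.2 or 8.5 |
| B. One on Day -1, one on Day 1 | R2 | (R2 - R1)/2: mean 0, SD 2.1 or 4.2 | R2 - R2 = 0 for every subject |
| C. None on Day 1 | P | mean d, SD s√1.5 = 3.7 or 7.3 | mean d, SD 4.2 or 8.5 |

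The mean of R1 and R2 is the baseline for blood pressure and heart rate. The last pre-dose reading is the baseline for temperature and respiratory rate. A simulation of 20,000 subjects per setting agreed. In A and B the literal rule gave mean changes within 0.08 of zero at every d. In C the mean change equalled d up to simulation error.

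**Step 5: the same rule limited to readings after the dose.** Against the two-reading baseline, the mean change was within 0.1 of d in all three schedules. For example, in schedule A with s = 3, d = +10 gave 10.04 and d = -20 gave -20.02.

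**Step 6: partial occurrence.** If a fraction f of an arm has a Day 1 pre-dose reading and d is common to all, the reported mean is (1 - f) × d. With f = 0 it is d, and with f = 1 it is 0. With 6 of the 18 nirsevimab subjects and d = 10, it is (1 - 6/18) × 10 = 6.7.

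**The case against.** The strongest reply is that the row label settles the matter. In Tables 2 and 3 the first column could be read as carrying the relation to dose and the second only the calendar day. Section 4.2.2.4 also applies change from baseline to post-baseline measurements, and Section 3.3.1.2 defines change as a post-baseline value minus baseline. A pre-dose reading in the post-dose row contradicts all three. The allocation sentence is also weak evidence the other way: screening and Day -1 readings have no row in Table 2 either, so that sentence cannot be taken literally for vital signs.

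This shows the intent, and it stands to that extent. It does not remove the conflict, because the SAP never says that the label overrides the window or that pre-dose readings are removed before the tie rule is applied.

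The second reply is that the SAP does not state that a pre-dose reading is taken on Day 1. That stands fully, and the point is conditional on it. The post-dose qualifier suggests that such readings exist. An unscheduled pre-dose reading on the dosing date would have the same effect, since Section 3.3.3 lets unscheduled data enter the windows.

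The third reply is that little is lost. All observed results are listed, worst post-baseline increases and decreases are listed, and AESIs are collected from dosing. None of these depends on the windowed record, and no statistical test is planned. This also stands and limits the severity.

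**Conclusion.** The defect is real but conditional. The window and tie rule, applied as written, select a pre-dose reading for the Day 1 post-dose row in any subject who has one on the dosing date. The number affected lies between 0 and all of the approximately 24 subjects, and the SAP alone does not say where. For those subjects the mean Day 1 change is about zero regardless of the true effect. Individual changes in blood pressure and heart rate need not be zero: where the selected reading is one of the two baseline readings, they equal half the difference between those two. Only the Day 1 row of a descriptive table is affected. The severity is minor to moderate.

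A reader might infer three stronger points that the document does not support:

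- **That the Day 1 table certainly reports pre-dose values.** This needs a Day 1 pre-dose reading, which the SAP leaves to the protocol, and a programmer who ignores the row label.
- **That later Day 1 readings are lost and each time point needs its own row.** The SAP does not say that several post-dose readings are scheduled on Day 1. Section 4.2.2.4 speaks of scheduled time-points in one place and scheduled study visits in another.
- **That setting a single reading against a two-reading baseline biases later visits.** The SAP states neither replicate readings at those visits nor any systematic difference between first and second readings.

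**What to change.** In Table 2, define the Day 1 post-dose row as Study Day = 1 and assessment date/time after dosing. Add to Section 3.3.2 that pre-dose readings are excluded from all post-baseline windows before the tie rule is applied.

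The cost is one line of SAP wording and one programming condition. No new data should be needed: the tie rule already relies on assessment time, and the TESAE definition in Section 4.2.2.1.1 already relies on the time of administration. If no pre-dose reading was taken on Day 1, the change alters no result and only brings the rule into line with its label.
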